### **Data analysis:**

Each variable was inspected for extreme outliers (i.e., data points that fell more than 4 standard deviations [SD] away from the mean) using summary statistics and box plots. An extreme outlier was excluded from the final analysis. Normality of the variables was determined based on skewness and kurtosis. Number that is greater than +1 or lower than -1 indicate a substantially skewed distribution. For kurtosis, if the number is greater than +1, the distribution is too peaked and less than -1 indicates a distribution that is too flat. If the distribution was found to deviate from normality, non-parametric statistical analysis was conducted.

Descriptive statistics described the study sample for age, sex, height, weight, race, current medication, education level, exercise level, DHI, ABC, history of falls, MoCA and HI- MoCA. To determine if the groups are similar with respect to background measures and demographics a comparison of the three groups Normal hearing, Mild BHL and > Moderate BHL (moderate, moderately-severe, severe and profound) was done using one-way analysis of variance (ANOVA) or non-parametric Kruskal-Wallis Test for continuous measures and Chi-square analyses for categorical measures (e.g., gender).

For Aim #1: Compare single task (=ST) gait parameters between individuals age and education-matched with Mild BHL, > Moderate BHL and controls with Normal hearing and Aim #3: Compare the effect of a cognitive task on gait parameters (=DT) between age and education-matched people with Mild BHL, > Moderate BHL and control with Normal hearing: For the primary outcome measure, gait speed and its variability, and secondary outcome measures (stride length, stride time and their variability) during the 1-min walk, a mixed model repeated measures (RM)- ANOVA was conducted with 1 within-factor (task) of 2 levels (ST and DT ['subtraction 3']) and 1 between factor (group) of 3 levels (Normal hearing, Mild BHL, Moderate BHL). When the distributions were found to deviate from normality the Kruskal-Wallis' test was conducted for a between-group comparison and the Wilcoxon signed-rank test for a within-group comparison. Since I had a significant difference with age, I adjusted for age the ANOVA comparison.

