Partial Eta Square (PET) Effect Size was reported for each main effect and interaction (small effect, PET  $\geq 0.08$ ; middle effect, PET  $\geq 0.20$ ; and high effect, PET  $\geq 0.32$ ). P-values with a value of  $p < 0.05$  were considered statistically significant. Bonferroni corrections were applied to post hoc comparisons as applicable.

For Aim #2: Compare cognitive function (i.e., the Neurocognitive Index) between individuals age and education-matched with Mild BHL, > Moderate BHL and controls with Normal hearing. One way ANOVA (or non-parametric Kruskal-Wallis Test) was used to compare the Neurocognitive Index between the three groups. Moreover, one way ANOVA (or non-parametric Kruskal-Wallis Test) was used to compare the secondary outcome measures, i.e., Composite Memory, Verbal Memory, Visual Memory, EF, Cognitive Flexibility, Complex RT, Working Memory and Sustained Attention and the cognitive ST and DT performance. I used one-way ANOVA with the dependent variable, the cognitive domain (Neurocognitive Index or any of the secondary outcome measures), and group as independent variable. For the raw scores I used the ACNOVA to adjust for age since we had significant age difference and these results do not present an age-matched score. Cohen's d effect size was calculated per comparison and was defined 'small' effect size as  $d = 0.2$ , 'medium' effect size as  $d = 0.5$  and a 'large' effect size as  $d = 0.8$ .

For Aim #4: Explore whether cognitive performance (i.e., the Neurocognitive Index) is correlated with DTC per group. One way ANOVA (or non-parametric Kruskal-Wallis Test) was used to compare the DTC between the three groups. Correlations between the cognitive domains and DTC were assessed using Pearson's correlation (or its non-parametric equivalent Spearman's, if the distributions are found to deviate from normality) for continuous variables. Pearson's correlation for each comparison was defined as 'little to none' for  $r = 0-0.24$ , 'fair' for  $r = 0.25-0.49$ , 'moderate to good' for  $r = 0.50-0.74$  and 'good to excellent' for  $r = 0.75-1.00$ . SPSS version 27 IBM (NY, US) was used for all statistical analysis.

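### Significance tests cannot show that the three non-randomised hearing groups are similar, and significance is the main stated reason for adjusting for age alone

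*Combined protocol and SAP*

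**What the plan says.** The three groups are defined by hearing status, not by randomisation: "Normal hearing, Mild BHL and > Moderate BHL (moderate, moderately-severe, severe and profound". The background measures are "age, sex, height, weight, race, current medication, education level, exercise level, DHI, ABC, history of falls, MoCA and HI- MoCA".

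The Data analysis section gives the purpose of the background tests directly: "To determine if the groups are similar with respect to background measures and demographics a comparison of the three groups". The tools are one-way ANOVA or "non-parametric Kruskal-Wallis Test for continuous measures and Chi-square analyses for categorical measures". The only significance criterion in the document is "P-values with a value of $p < 0.05$ were considered statistically significant". No margin, standardised difference or confidence interval is given for any background measure.

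Covariate adjustment appears twice, each time for age only. For gait (Aims #1 and #3): "Since I had a significant difference with age, I adjusted for age the ANOVA comparison". For the raw cognitive scores (Aim #2), an analysis of covariance was used "to adjust for age since we had significant age difference and these results do not present an age-matched score", which gives a second, substantive reason besides significance. No covariate is named in advance on subject-matter grounds.

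The aims describe "individuals age and education-matched with Mild BHL, > Moderate BHL and controls with Normal hearing". No matching procedure or tolerance is given, and age nevertheless differed significantly.

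**The concern.** A test of no difference answers a different question from the one the plan asks. In a small sample a p-value above 0.05 may mean that the groups are alike or that the test had little power, and the p-value alone cannot separate the two. In an observational comparison, confounding depends on the size of an imbalance and on how strongly the variable relates to the outcome, not on its p-value.

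The same criterion reaches the outcome models, because significance is the stated trigger for adjusting for age. Sex, height, weight, education and exercise level are all recorded and could plausibly relate to gait or cognition, yet none is in a model. A moderate imbalance in one of them that the test missed would stay in the group contrast, where it could pass for a hearing effect or hide one.

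**Working it through.** The document gives no sample size, power or detectable difference, so there is no figure of its own to reproduce.

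**Inputs.** From the Data analysis section: three groups, omnibus one-way ANOVA, α = 0.05. Assumed: 10 to 30 equal-sized groups' members per group (the procedures are headed as a pilot study), SD = 1, and a largest gap between groups of 0.5 SD. The plan calls d = 0.5 medium, but for outcome comparisons, so its use for a background variable is also an assumption.

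**Miss rate.** Power comes from the noncentral F distribution with 2 and 3n − 3 degrees of freedom and λ = n × Σ(μᵢ − μ̄)².

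- One group shifted (0, 0, 0.5): μ̄ = 0.167, Σ = 2 × 0.0278 + 0.1111 = 0.1667.
- Evenly graded (0, 0.25, 0.5): μ̄ = 0.25, Σ = 0.0625 + 0 + 0.0625 = 0.125.

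| n per group (assumed) | λ, one shifted | missed | λ, graded | missed |
|---|---|---|---|---|
| 10 | 1.67 | 82% | 1.25 | 86% |
| 20 | 3.33 | 66% | 2.50 | 74% |
| 30 | 5.00 | 51% | 3.75 | 62% |
| 40 | 6.67 | 38% | 5.00 | 51% |
| 60 | 10.00 | 19% | 7.50 | 32% |

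Detection first reaches 50% at 31 per group (one shifted) or 41 (graded), and 80% at 59 or 79.

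Unequal groups give a similar picture across the two patterns: 10/10/20 misses 75–81%, 30/15/15 misses 71–73%, and 20/20/40 misses 51–65%.

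**Categorical check.** For proportions 50/50/74%, p̄ = 0.58 and λ = n × 0.0384 / (0.58 × 0.42) = 0.158n. The noncentral chi-square power is 0.185, 0.336 and 0.480 at n = 10, 20 and 30, so about 81–82%, 66% and 52% are missed.

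**Effect on the group comparison.** Take one covariate that correlates 0.5 with the outcome, the third group shifted 0.5 SD, and no true hearing effect. Never adjusting leaves 0.5 × 0.5 = 0.25 SD of bias. Adjusting only when the covariate's ANOVA gives p < 0.05 (4,000 simulated studies) leaves a mean bias of 0.163, 0.121 and 0.080 SD at n = 10, 20 and 30. This is less than the miss rate times 0.25 (0.82 × 0.25 = 0.205 at n = 10), because the samples in which the test misses tend to show a smaller observed imbalance. The group test rejects the true null 5.1–6.3% of the time.

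**Reach across the aims.** This bias sits in a between-group contrast, so it applies to Aims #1 and #2. In the task-by-group contrast of Aim #3, a covariate that acts equally on single-task and dual-task walking cancels within person.

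**The case against.** The strongest reply is that testing was not the only control. The aims call for matching on age and education, and age was adjusted for once it was seen to differ. For raw cognitive scores there was also a substantive reason. This stands in part. Matching is not claimed for sex, height, weight or exercise level, and by the plan's own account it did not hold for age.

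A second reply is that the miss rates depend on a sample size the document does not give. That is correct. A 0.5-SD gap is missed most of the time only up to about 30 per group (one group shifted) or 40 (graded). If each successive group differed by 0.5 SD, 1.0 SD overall, power would already exceed 50% at 11 per group. The step from non-significance to similarity is invalid at any sample size; only its practical cost shrinks.

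Several stronger readings are tempting, and the document does not support them:

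- A reader might infer that the non-significant variables were declared balanced, or that a particular hidden imbalance exists. The text reports a test result for age only and never says what was concluded about the others.
- A reader might infer a clearly inflated false-positive rate. With one covariate it is about 5–6%. It reaches about 9% or slightly more only if four covariates are all shifted and all bias the outcome in the same direction; with the directions offset it is about 5%. Nothing in the document points to such alignment.
- A reader might compute 1 − 0.95¹³ = 0.49 as the chance of at least one spurious background difference. The 13 listed measures are not independent: MoCA and HI-MoCA are alternatives in the procedure list, DHI is capped at 10 by eligibility, and height, weight and sex are related. An unneeded covariate would in any case not bias the hearing comparison.

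**Conclusion.** The point holds in a limited form. The plan uses tests of no difference to decide whether non-randomised groups are similar, and significance is the trigger for adjusting for age, the sole covariate. In groups of about 10 to 30, a 0.5-SD imbalance on one variable goes undetected 51–82% of the time (one group shifted) or 62–86% (graded).

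The cost for one such covariate is bias rather than error-rate inflation: about 0.16 SD at 10 per group, falling to 0.08 SD at 30, in the group comparisons of Aims #1 and #2. The Aim #3 interaction is exposed only where the covariate changes the effect of the cognitive task.

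These sizes rest on the assumed sample size, the 0.5-SD gap and the 0.5 correlation. The logical point rests on none of them. It is worth correcting because the remedy uses data already collected.

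**What to change.** Replace the sentence on group similarity with wording such as: Group balance is described by pairwise standardised mean differences, or differences in proportions, with 95% confidence intervals for each background variable; non-significance is not taken as evidence of similarity, and p-values are not used to choose covariates.

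Add a sensitivity analysis of the Aim #1 to #3 models with a short list of already collected covariates, chosen on subject-matter grounds and not plausible consequences of hearing loss. Age, sex, education and, for gait, height are examples. They enter whatever their p-values. If the hearing estimate changes materially, the report should say so. The Kruskal-Wallis and Wilcoxon fallbacks carry no covariates, so the sensitivity model must be a separate regression-type model where those were used.

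A numerical trigger, such as adjusting whenever a pairwise standardised difference exceeds 0.25, would not be a good substitute. In three truly identical groups, a continuous variable crosses that line in at least one pair about 85%, 71–72% and 60% of the time at 10, 20 and 30 per group.

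The cost is one descriptive table, one additional model per outcome and a few degrees of freedom. The report also gives up calling the groups similar on the strength of p > 0.05. No new participants or measurements are needed, and the main analysis stays in place.

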13. TMT A & B
14. Practice trial: Walking back and forth the corridor

15. Randomized Trial- each trial will be done 1 time (without hearing aid):

1. Single cognitive task sub1 - [Baseline] while sitting (serial subtraction of 1) + record with phone
2. Single cognitive task sub3 - [Baseline] while sitting (serial subtraction of 3) + record with phone
3. Single motor – [Baseline] Walking on the ground for 1 min a 10 m long corridor – recording with a stopwatch
4. Dual task cognitive sub1 (DT\_sub1) - serial subtraction of 1 + #3 - recorded with stopwatch + record with phone
5. Dual task cognitive sub3 (DT\_sub3) - serial subtraction of 3 + #3 - recorded with stopwatch + record with phone

Using REDCAP:

16. DEMOGRAPHIC questionnaire (descriptive)
17. ABC – In healthy young adults ask: “have you never had any concern regarding: balance?” – if yes- fill up the questionnaire. (descriptive)

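### Aim 1 asks whether groups differ in single-task gait, but the shared RM-ANOVA's group terms test the task average and the task difference, and no single-task test is named

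*Combined protocol and SAP*

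**What the plan says.** All of this is in the Data analysis section of the combined protocol and SAP unless noted.

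- Aim 1 is "Compare single task (=ST) gait parameters between individuals age and education-matched with Mild BHL, > Moderate BHL and controls with Normal hearing".
- Aim 3 is "Compare the effect of a cognitive task on gait parameters (=DT) between age and education-matched people" in the same three hearing groups.
- Both aims receive the same analysis: "a mixed model repeated measures (RM)- ANOVA was conducted with 1 within-factor (task) of 2 levels (ST and DT ['subtraction 3" and so on, with group as the three-level between-subject factor. It is applied to gait speed and its variability (primary) and to stride length, stride time and their variability (secondary), with adjustment for age.
- If distributions are not normal, the Kruskal-Wallis "test was conducted for a between-group comparison and the Wilcoxon signed-rank test for a within-group comparison".
- On reporting: "Partial Eta Square (PET) Effect Size was reported for each main effect and interaction".
- On follow-up tests: "Bonferroni corrections were applied to post hoc comparisons as applicable".

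No sentence says which term or contrast answers Aim 1. Under Aim 2, by contrast, the list of outcomes for one-way ANOVA or Kruskal-Wallis ends with "Working Memory and Sustained Attention and the cognitive ST and DT performance", so there the task condition is named. The single-task walk is a separate trial in the test protocol (item 15, "Walking on the ground for 1 min a 10 m long corridor"), so ST gait values exist for a direct group comparison.

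**The concern.** Aim 1 is about one condition, walking without a second task. The model pools that condition with dual-task walking. Its group main effect mixes the ST difference with the dual-task effect, and its interaction removes the ST level altogether. A reader looking for the Aim 1 result on the primary outcome finds two group terms, neither of which answers it, and no rule that leads from a significant interaction to an ST comparison.

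If the group main effect is taken as the Aim 1 result, the error can go either way. A deficit seen only under dual task can look like a single-task gait deficit. A deficit that is larger in single-task walking can be diluted and missed. Because the contrast is unnamed, it can also be chosen after the results are known.

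**Working it through.** **No figure to reproduce.** The documents state no sample size, SD, ST-DT correlation, expected effect or power. The first step below needs none of these; the later steps rest on assumed values.

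**1. What the two group terms test.** With two task levels, the between-subject part of the model uses each person's average and the within-subject part uses each person's difference.

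- Group main effect: one-way test on (ST + DT)/2. Since (ST + DT)/2 = ST + (DT - ST)/2, the expected group difference equals the ST difference plus half the interaction.
- Interaction: one-way test on DT - ST.

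A check on one simulated data set (3 groups of 20) gave:

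| Quantity | F |
|---|---|
| RM-ANOVA group term | 0.8017 |
| One-way ANOVA on (ST + DT)/2 | 0.8017 |
| RM-ANOVA interaction | 11.578 |
| One-way ANOVA on DT - ST | 11.578 |
| One-way ANOVA on ST alone | 0.108 |

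The age covariate takes one value per person, so it leaves this split unchanged.

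**2. Assumed inputs for size.** n = 15 to 30 per group; SD 0.2 m/s in both tasks; ST-DT correlation r = 0.5 to 0.8; deficit graded 0, half and full across the three groups; alpha 0.05; no age covariate.

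Power comes from the noncentral F with 2 and 3(n - 1) df and noncentrality λ = n × Σ(group mean - grand mean)² / SD². The error SDs are:

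- ST: 0.2
- Average: 0.2 × √((1 + r)/2)
- Difference: 0.2 × √(2(1 - r))

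Worked cell: DT-only deficit 0.10 m/s, n = 15, r = 0.5.

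- Average: group means 0, 0.025, 0.05; sum of squares 0.00125; variance 0.04 × 0.75 = 0.03; λ = 15 × 0.00125/0.03 = 0.625; power 9.6%.
- Difference: group means 0, 0.05, 0.10; sum of squares 0.005; variance 0.04 × 1 = 0.04; λ = 15 × 0.005/0.04 = 1.875; power 20.1%.
- ST: no difference, so 5%.

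At equal SDs the average and the difference are independent, so P(main effect significant, interaction not) = 0.096 × (1 - 0.201) = 7.7%. With no group difference at all it is 0.05 × 0.95 = 4.75%.

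**3. Deficit under dual task only** (an ST test rejects in 5%). Each pair is n = 15, n = 30.

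| r | DT deficit (m/s) | Main effect % | Interaction % | Main without interaction % |
|---|---|---|---|---|
| 0.5 | 0.10 | 9.6, 15.1 | 20.1, 38.1 | 7.7, 9.4 |
| 0.5 | 0.20 | 25.7, 48.9 | 65.4, 93.6 | 8.9, 3.1 |
| 0.8 | 0.10 | 8.8, 13.3 | 44.8, 77.3 | 4.9, 3.0 |
| 0.8 | 0.20 | 22.0, 41.8 | 97.0, 100 | 0.7, 0.0 |

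Over the full grid of 18 cells (r 0.5, 0.7, 0.8; n 15, 20, 30; deficit 0.10, 0.20), the last column exceeds 4.75% in 9.

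**4. Deficits in both tasks.** Power %, n = 15, n = 30.

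| Pattern (m/s) | ST test | Main effect, r = 0.5 | Main effect, r = 0.8 |
|---|---|---|---|
| ST 0.20, DT 0.10 | 65.4, 93.6 | 52.3, 84.8 | 44.8, 77.3 |
| ST 0.20, DT 0.20 | 65.4, 93.6 | 78.5, 98.2 | 70.3, 95.8 |

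In the first row the main effect loses 8.8 points (93.6 - 84.8) to 20.6 points (65.4 - 44.8). In the second it gains 2.2 points (95.8 - 93.6) to 13.1 points (78.5 - 65.4).

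**5. The two terms cannot locate the deficit.** With n = 20, r = 0.8 and group means of 0, -0.4 and -0.8 SD in one task only, the main effect rejects in 19.6% and the interaction in 94.6%, whether the affected task is ST or DT. An ST test rejects in 58.9% in the first case and 5% in the second.

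**The case against.** The strongest reply is that this is a gap in reporting, not a shown wrong analysis. Nothing in the text says the group main effect was read as the Aim 1 result. The sentence on effect sizes says where partial eta squared was given and is not a full list of tests. A two-by-three model with post hoc comparisons is a usual route to group contrasts at ST. Kruskal-Wallis takes one value per person, so in practice it may well have been run on ST and DT separately. All of this stands as a possibility, but the text confirms none of it: the post hoc tests are not listed and the fallback names no task level.

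A second reply concerns size, and much of it stands. Every rate rests on assumed inputs, without the age covariate and with equal SDs. A main effect with no warning from the interaction occurs in 0-9% of the dual-task-only cells, at most about 4.7 points above chance. At r = 0.9 it falls to 0-2.1%, below chance in every cell. When deficits are equal the main effect is the more powerful test. But a significant interaction only warns; no stated step then tests ST. The main effect is a fair stand-in only if the group difference is the same in both tasks, which is what Aim 3 sets out to examine.

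The group comparison of DTC under Aim 4 does not help. The text does not define DTC. If it measures change from ST to DT, it largely repeats the interaction.

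Finally, this is a pilot and the remedy is short. That limits the cost of the fix, but gait speed is still the primary outcome.

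**Conclusion.** The concern holds. As written, the analysis does not name a test of the Aim 1 question on the primary outcome, and the two group terms it reports test other quantities. That part is algebra and needs no assumption.

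The practical effect arises only if the main effect was used for Aim 1, and it can go in either direction. Under the assumed inputs, rejection rates are 9-49% for the main effect against 5% for an ST test when only dual-task gait differs. Power is 45-85% against 65-94% when the ST deficit is twice the DT deficit, and 70-98% against 65-94% when the two are equal. The omission is certain; its consequence for this study's results cannot be judged from the documents. It should be corrected. Aim 3 is unaffected, because the interaction is the right term for it.

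**What to change.** State one test per aim in the Data analysis section.

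- **Aim 1:** the age-adjusted group effect at task = ST, either as an ANCOVA on the ST value or as the simple effect from the mixed model, with Bonferroni-corrected pairwise comparisons. Where the fallback applies, Kruskal-Wallis on ST values.
- **Aim 3:** the group-by-task interaction.
- Do not present the group main effect as the Aim 1 result.
- If ST tests were already run as post hoc or fallback tests, say so and give the task level. If the ST contrast was not pre-specified, label it as added.

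The cost is two sentences and at most one extra model for each of the six gait outcomes (speed, stride length, stride time and the variability of each) on data already collected. The Aim 1 result may change in either direction. If the deficits are in fact equal in the two tasks, the ST test gives up about 2 to 13 points of power relative to the average in the cells shown.

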2. SIGN CONSENT
3. ETDRS- eyes check (screening)
4. MONOFILAMENT TEST- put the shoes on (screening)
5. Vestibular examination: (screening)- Dizziness Handicap Inventory (DHI) questionnaire (in REDCAP)
6. Auditory screening for the control group (screening older controls for ARHL rather than a full audiogram to everyone).

---

Exclusion due to one of the followings:

- ETDRS - visual impairment above 20/63
- MONOFILAMENT - No protective sensation at the bottom of their feet.
- DHI- Participants will be included with a score of 10 or below indicating no more than minimal dizziness.
- Auditory screening – participants in the control group that will exhibit a PTA higher than 40 dB (0.5–4 kHz) in the better ear (moderate HL and above) will be excluded.

---

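### Aims 1–3 call the hearing groups age-matched although age differed significantly, and several analyses state no age adjustment

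*Combined protocol and SAP*

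**What the plan says.** The Data analysis section words three of its four aims as comparisons of groups that are "age and education-matched":

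- Aim #1: "Compare single task (=ST) gait parameters between individuals age and education-matched with Mild BHL, > Moderate BHL and controls with Normal hearing".
- Aim #3, on the dual task: "between age and education-matched people with Mild BHL, > Moderate BHL and control with Normal hearing".
- Aim #2, on cognition: "between individuals age and education-matched with Mild BHL, > Moderate BHL and controls with Normal hearing".

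The section also tests whether the three groups are alike on background measures and demographics, and lists age and education level among its descriptive variables. On age it reports the outcome: "Since I had a significant difference with age, I adjusted for age the ANOVA comparison". Under Aim #2 it gives the same reason for analysing the raw cognitive scores by ANCOVA, adding that those scores are not age-matched ones.

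Neither the numbered procedure nor the exclusion list gives a matching procedure (variables, caliper, ratio, individual or frequency matching) or an age range for eligibility. Two steps show that a range of ages was expected. Item 17, on the ABC questionnaire, begins "In healthy young adults ask", and item 6 speaks of "screening older controls for ARHL rather than a full audiogram to everyone".

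**The concern.** A design described as age-matched tells the reader that age was dealt with before analysis. If the groups differ in age, that assurance is gone, and age is controlled only where an analysis includes it or the outcome is already normed for it. The plan itself treats age as needing adjustment in its gait and raw-score analyses.

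Two things are at stake. A conclusion that repeated the wording of the aims would overstate how well age was controlled. And any between-group comparison with no age term relies on a balance that the plan's own test did not find, so a hearing-group difference there could partly be an age difference.

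**Working it through.** **1. Is there a figure to reproduce?** No. The documents give no group ages, SDs, sample size or p-value for age. The main check is therefore of the text, and steps 4 to 6 are illustrations on assumed inputs.

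**2. The two statements side by side.** Aims #1 to #3 assert matching on age and education. The analysis text reports a significant age difference twice, once for gait and once for the raw cognitive scores. Both cannot describe the achieved sample, so the age half of the label fails. No education result is given, so the education half is neither supported nor contradicted.

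**3. Where age control is stated.**

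| Analysis | Age control stated |
|---|---|
| Gait, repeated-measures ANOVA (Aims #1, #3) | Yes, adjusted for age |
| Gait, Kruskal-Wallis fallback between groups | None |
| Raw cognitive scores, ANCOVA (Aim #2) | Yes |
| Neurocognitive Index, one-way ANOVA (Aim #2) | No age term; the remark about raw scores implies that other scores are age-normed, but the section does not say which |
| Cognitive outcomes, Kruskal-Wallis fallback (Aim #2) | None, except through norming |
| DTC between groups, ANOVA or Kruskal-Wallis (Aim #4) | None |
| Correlations with DTC (Aim #4) | None |

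The fallback applies whenever skewness or kurtosis lies beyond ±1, and Kruskal-Wallis as ordinarily run takes no covariate. The Wilcoxon signed-rank test compares people with themselves, so an age difference between groups does not bias it. The Aim #4 correlations are computed per group. Matching between groups would not have removed age from them in any case; that needs an age term.

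**4. Could the age difference be trivial?** Assume three equal groups of n (the study is labelled a pilot; n of 8 to 40 is an assumption). At α = 0.05, with F the critical value on 2 and 3n − 3 degrees of freedom:

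- smallest significant η² = 2F / (2F + 3n − 3)
- gap if one group differs from the other two = √(1.5 × 2F / n) within-group SD
- gap between the extreme groups if the means are evenly spaced = √(2 × 2F / n) within-group SD

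| n per group | F | η² | One group off | Evenly spaced |
|---|---|---|---|---|
| 8 | 3.47 | 0.248 | 1.14 | 1.32 |
| 10 | 3.35 | 0.199 | 1.00 | 1.16 |
| 20 | 3.16 | 0.100 | 0.69 | 0.79 |
| 30 | 3.10 | 0.067 | 0.56 | 0.64 |
| 40 | 3.07 | 0.050 | 0.48 | 0.55 |

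For n = 10: 2 × 3.35 = 6.70; η² = 6.70 / 33.70 = 0.199; √(1.5 × 6.70 / 10) = 1.00. At these sizes a significant result needs an observed gap of about half an SD or more, which is not effective matching.

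**5. Bias in an unadjusted contrast.** Bias in outcome SD = age gap (SD) × age–outcome correlation. With an assumed gap of 1 SD: 1 × 0.3 = 0.3 and 1 × 0.5 = 0.5. On the Cohen's d scale given under Aim #2, this runs from just above small (0.2) to medium (0.5). The gait analyses report partial eta squared, so that comparison does not carry over to them.

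**6. Precision cost of adjusting.** For two equal groups, variance inflation = 1 + gap²/4: 1.25 at 1 SD and 2.0 at 2 SD. This is a two-group approximation to a three-group design.

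**The case against.** The strongest reply is that the plan hides nothing. It reports the age difference, adjusts the gait ANOVA and the raw cognitive scores for it, and implies that the remaining cognitive scores are age-normed. The aims may simply record the design as intended, with the past-tense text recording what happened. Much of this stands. The imbalance is disclosed, and the parametric primary gait analysis carries an age adjustment. But the documents do not present the wording of the aims as intention only, and disclosure does not supply an age term to the analyses that lack one.

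Three stronger readings are tempting, and the documents do not support them.

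- A reader might infer that the whole matching claim is false. Only age is contradicted.
- A reader might infer from the young-adult and older-control steps that young people were concentrated in one hearing group, so that the age term extrapolates. The text does not say which group the young adults joined, how many there were, or whether they were analysed. A wide age range is compatible with matching. Poor overlap is a possibility to check.
- A reader might apply the 0.3 to 0.5 SD bias to the primary gait result. It applies to an unadjusted contrast only.

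It is also fair to say that a subset restricted to shared ages may be too small to settle much in a pilot.

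**Conclusion.** The point holds for age. The plan's own report shows that age matching was not achieved, yet three aims still assert it. Age is adjusted for in the gait ANOVA and the raw-score ANCOVA. The Kruskal-Wallis fallback, for outcomes that are not age-normed, and the Aim #4 DTC comparison and correlations have no valid age control.

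The contradiction rests on the text alone. Its size does not: about 0.3 to 0.5 SD for an unadjusted contrast assumes a 1 SD age gap and an age–outcome correlation of 0.3 to 0.5, and the true gap cannot be worked out from the documents. The documents contain no conclusion worded as age-matched, so the risk to reporting is one to prevent. This should be corrected, because it changes what can be concluded and costs little.

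**What to change.** 1. Remove *age-matched* from Aims #1 to #3 and from any conclusion, and state that age balance was not achieved. Keep *education-matched* only if the education comparison supports it.
2. Use *age-adjusted* only for analyses that contain an age term. A blanket label would be untrue for the Neurocognitive Index ANOVA, the Kruskal-Wallis fallback and Aim #4. State which cognitive scores are age-normed and describe them that way.
3. Use an age-adjusted method where outcomes that are not age-normed go to the non-parametric route (for example rank-based ANCOVA, or ANCOVA on a transformed outcome). In Aim #4, do the same for the DTC comparison and use partial correlations given age.
4. Report the age range in each group, and add one sensitivity analysis restricted to the age range shared by all three groups, stating its reduced sample.

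The cost is SAP wording, an age table and some reruns on data already held. Adjustment may cost precision if the age gap is large, and the restricted analysis will have fewer participants, so it should be read as a check on the main result and not as a replacement for it.
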